The effect of different altitude levels on spinal anesthesia in cesarean section surgery; Comparison of anesthesia parameters and hemodynamic changes

DEMOGRAPHIC DA	ATA;									
Age										
Weight/Height/ BMI										
(m-kg-kg/m2)										
ASA										
INTRAOPERATIVE	FOLLOW	′-UP;								
	Basal	After Spinal 3.minute	5.mn	10.mn	15.mn	30.mn	45.mn	60.m n		
HR (Heart rate)										
MAP (mean arterial pressure) mmHg										
SpO2(Saturation)										
Number and du	ration	of spinal a	nesthes	sia						
applications										
The value meas	sured w	rith a pH n	neter							
Sensory block T6	transit	time								
Highest level of s	sensory	block								
MB (modified br	omage)	scale; time	e to read	ch score	1					

MB (modified bromage) scale; time to reach score 2	
MB (modified bromage) scale; time to reach score 3	
Number of hypotensive episodes requiring	
ephedrine	
Number of episodes of bradycardia requiring	
atropine	
Number of episodes of nausea requiring Zofer	
Surgery time	
Anesthetic complications	

POSTOPERATIF TAKIP;

	1.hour	2.hour	3.hour	4.hour	5.hour
Sensory blockade end time					
Motor blockade end time					
Nausea-vomiting					

Postdural puncture headache follow-up (YES/NO)

1.day	7.day

Modified bromage scale

0	No paralysis, the patient can fully flex the foot and knee
1	Can only move knee and feet, can't lift leg straight
2	Can't flex knee, can only move foot
3	He cannot move his foot joint or big toe, he has complete paralysis

Nausea-vomiting 'Verbal Descriptive Scale'

1:	Mild nausea
2:	Moderate nausea
3:	One time vomiting
4:	Multiple vomiting

Study design

Standard noninvasive blood pressure, heart rate (HR), electrocardiogram (ECG) findings, peripheral oxygen saturation (SpO2) will be monitored for all patients brought to the operating room. 2.2 cc of bupivacaine will be administered after entering the L4-5 space under sterile conditions in the sitting position and seeing the cerebrospinal fluid flow. The shastaol will be quickly tilted laterally. Sensory block level will be checked with pinprick test and surgery will be started by recording the time to reach T6 dermatome. Mean arterial pressure, heart rate and peripheral oxygen saturation will be recorded before the procedure (baseline), at the 3rd, 5th, 10th, 15th, 30th, 45th and 60th minutes after the procedure. The number and duration of spinal anesthesia applications, the duration of sensory block formation in the T6 dermatome, the time to reach each score of the Modified bromage score scale, the operation time (the time from the beginning of the surgical incision to the completion of the surgery), the highest level of sensory block, and anesthetic complications will be recorded. Patients with a sensory block level below T6 in the recovery room and a Modified Aldrete score above 8 will be taken to the ward. During the postoperative period, sensory blockade time (time to feel the S2 dermatome), motor blockade time (time to have a MB score of 0) will be recorded every hour in the ward. Nausea and vomiting in the postoperative period will be followed up with the Verbal Descriptive Scale. On the first and seventh days after the operation, the patients will be questioned by the researcher for postdural puncture headache (PDPH, increased pain intensity when standing up from the supine position) by phone call.

The effect of different altitude levels on spinal anesthesia in cesarean section surgery; Comparison of anesthesia parameters and hemodynamic changes

Statistical Analysis Plan

One Way ANOVA Power Analysis

| | | | _ | | | Std Dev | Standard | _ |
|---------|---------|---|-------|---------|---------|----------|-----------|--------|
| | Average | | Total | | | of Means | Deviation | Effect |
| Power | n | k | N | Alpha | Beta | (Sm) | (S) | Size |
| 0,81163 | 31,00 | 3 | 93 | 0,05000 | 0,18837 | 18,37 | 55,35 | 0,3319 |

References

Numeric Results

Desu, M. M. and Raghavarao, D. 1990. Sample Size Methodology. Academic Press. New York. Fleiss, Joseph L. 1986. The Design and Analysis of Clinical Experiments. John Wiley & Sons. New York. Kirk, Roger E. 1982. Experimental Design: Procedures for the Behavioral Sciences. Brooks/Cole. Pacific Grove, California.

Report Definitions

Power is the probability of rejecting a false null hypothesis. It should be close to one. n is the average group sample size. k is the number of groups. Total N is the total sample size of all groups combined. Alpha is the probability of rejecting a true null hypothesis. It should be small. Beta is the probability of accepting a false null hypothesis. It should be small. Sm is the standard deviation of the group means under the alternative hypothesis. Standard deviation is the within group standard deviation. The Effect Size is the ratio of Sm to standard deviation.

Summary Statements

In a one-way ANOVA study, sample sizes of 31, 31, and 31 are obtained from the 3 groups whose means are to be compared. The total sample of 93 subjects achieves 81% power to detect differences among the means versus the alternative of equal means using an F test with a 0,05000 significance level. The size of the variation in the means is represented by their standard deviation which is 18,37. The common standard deviation within a group is assumed to be 55,35.

Sample size; The minimum number of patients required to complete our study with 95% confidence level (α =0.05) and 80% power was calculated as 31 for each group, a total of 93. The IBM-Statistical Package for Social Sciences (IBM-SPSS Inc., Chicago, IL, USA) 22.0 program will be used in the analysis of the data obtained in the study. The conformity of the data to the normal distribution will be examined by the "Shapiro-Wilk test". Continuous variables will be expressed as mean and standard deviation or (median (25-75 percentile)) according to their distribution status, and categorical variables will be expressed as numbers and percentages. In the analysis of continuous variables, the 'One-Way Anova test' will be applied in cases where parametric test assumptions are met, otherwise the 'Kruskal-Wallis test' will be applied. Bonferroni or Games-Howell tests will be applied for post hoc comparisons. "Chi-square test" will be used in the analysis of categorical variables. "Analysis of Variance (ANOVA)" will be used for repeated measurements at different times between groups. Statistical significance level will be accepted as p<0.05.

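### Three altitude groups with no described randomisation are compared only by tests without covariates, so a difference in age, body size or ASA could be read as an altitude effect

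*SAP*

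**What the plan says.** The title names altitude level as the exposure, and the SAP plans three groups of 31. Neither document says how a patient comes to be in a group. Randomisation, matching, stratification and restriction are not mentioned, and the public files contain no eligibility section.

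The statistical paragraph of the SAP lists these tests:

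- For continuous outcomes, "the 'One-Way Anova test' will be applied in cases where parametric test assumptions are met, otherwise the 'Kruskal-Wallis test' will be applied", followed by Bonferroni or Games-Howell comparisons.
- A chi-square test that "will be used in the analysis of categorical variables".
- An ANOVA that "will be used for repeated measurements at different times between groups". The SAP does not say whether the group effect or the group-by-time interaction is the term of interest.

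It gives no covariate, adjusted model, stratified test or rule for baseline imbalance. The demographic block of the protocol's data form records age, "Weight/Height/ BMI" and ASA. Under Study design, mean arterial pressure, heart rate and oxygen saturation are recorded at eight times, from baseline to 60 minutes.

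The Summary Statements of the power analysis say: "The total sample of 93 subjects achieves 81% power to detect differences among the means". Of the spread of means they say "The size of the variation in the means is represented by their standard deviation which is 18,37", and of the residual spread "The common standard deviation within a group is assumed to be 55,35".

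**The concern.** An investigator does not ordinarily assign altitude, so nothing described in the design makes the groups alike in age, body size or ASA class. A factor that differs by altitude and also relates to an outcome moves the group means apart even if altitude does nothing. Every listed test would attribute that movement to altitude. Comparing the demographic variables across groups might reveal the imbalance, but it would not correct the outcome comparison.

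At stake is the question in the title. The variables needed for adjustment are already collected, but the plan makes no use of them in the outcome analyses. If covariates are chosen only after the data are seen, selective reporting becomes possible.

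**Working it through.** **1. The plan's own figure.** From the SAP: Sm = 18.37, S = 55.35, 31 per group, three groups, alpha 0.05. Then f = 18.37/55.35 = 0.3319 and the noncentrality is 93 × f² = 10.24. With 2 and 90 df the power is 0.8116, against the stated 0.81163. With 30 per group it is 0.797, so 31 is the minimum. The sample size is sound on its own inputs.

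**2. False-positive rate without adjustment.** Assumptions, none given in the documents: no altitude effect; one covariate rising evenly across the groups, with the end groups D within-group SDs apart; within-group correlation r with the outcome. The outcome means are then displaced by (−rD/2, 0, +rD/2) SD. The noncentrality is 31 × (rD)²/2 = 15.5(rD)², with 2 and 90 df. The spurious end-to-end difference in the SAP's units (outcome and unit not named) is r × D × 55.35. If the planned means are evenly spaced, the planned end-to-end difference is 2 × 18.37 × √1.5 = 45.0.

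| D | r | Noncentrality | False-positive rate | Spurious difference | Share of 45.0 |
|---|---|---|---|---|---|
| 0.5 | 0.1 | 0.039 | 5.3% | 2.8 | 6% |
| 0.5 | 0.2 | 0.155 | 6.1% | 5.5 | 12% |
| 0.5 | 0.3 | 0.349 | 7.6% | 8.3 | 18% |
| 1.0 | 0.1 | 0.155 | 6.1% | 5.5 | 12% |
| 1.0 | 0.3 | 1.395 | 16.4% | 16.6 | 37% |
| 1.0 | 0.4 | 2.480 | 26.4% | 22.1 | 49% |

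A correctly specified ANCOVA with three covariates gave 4.7% to 5.2% in simulation (20,000 runs per setting), consistent with 5%.

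**3. Would a baseline comparison show the imbalance?** The same F test on the covariate itself has noncentrality 15.5D². It is significant in 39% of trials at D = 0.5 and in 94% at D = 1.

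**4. Repeated measurements.** Simulated false-positive rates without adjustment, with eight times, within-patient correlation 0.5 and covariate coefficient 0.3 SD (10,000 runs per setting):

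| Covariate acts on | Term tested | D = 0.5 | D = 1 |
|---|---|---|---|
| Level at all times | Group-by-time | 5% | 5% |
| Level at all times | Group main effect | 9% | 23% |
| Fall after baseline | Group-by-time | 6% | 12% |
| Fall after baseline | Group main effect | 8% | 19% |

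A covariate entered without a time interaction leaves the group-by-time test as it was. With covariate-by-time terms, the 12% falls to about 5% to 6%.

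**5. Power of the adjusted test.** With three exactly balanced covariates the noncentrality is 93f²/(1 − R²), with 2 and 87 df. For the other rows, power was averaged over 4,000 simulated covariate sets. The rows with systematic imbalance take R² = 0.09, and linear means are evenly spaced group means.

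| Situation, f = 0.3319, N = 93 | Power |
|---|---|
| Exact balance, R² 0 or 0.10 | 81.1% or 85.2% |
| Chance imbalance only, R² 0 or 0.10 | 79.7% or 84.0% |
| D = 0.5, one covariate shifted, linear means | 81.8% |
| D = 0.5, all three shifted, linear means | 78.6% |
| D = 1, one shifted, linear means | 77% |
| D = 1, all three shifted, middle group differs | 84% |
| D = 1, all three shifted, linear means | about 65% |

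Covariate-by-time terms for three covariates cost 3 × 7 = 21 parameters, so the error df fall from 630 to 609. A group-by-time test with 80% power drops to 78% with uninformative covariates and chance imbalance. It drops to 70% with one covariate shifted by D = 1 and linear means.

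**The case against.** The premise is inferred. No group definitions or eligibility criteria are available, so restriction on BMI or ASA cannot be ruled out, and nothing shows that any recorded factor is a confounder here. Every r and D is assumed. With end groups half an SD apart the inflation is small. The 16% to 26% rates need a full 1 SD gap, which a demographic comparison would nearly always flag. All of this stands, and it makes the point conditional. It does not remove it: a flagged imbalance is still uncorrected, and a half-SD gap would usually go unflagged.

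The second objection is that adjustment has limits and a price. Simply adding covariates would not protect the haemodynamic group-by-time comparison. A log-scale ANCOVA does not suit a dermatome level or episode counts that can be zero. Categorical outcomes would remain unadjusted. Power can fall below the 80% target, most of all where large imbalance makes adjustment most wanted. This also stands. It limits full adjustment to the non-repeated continuous outcomes, calls for a separate provision for the repeated ones, and means that the loss must be stated.

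**Conclusion.** The point holds in conditional form and should be fixed. The plan has no covariate adjustment for a comparison in which no randomisation is described, although candidate covariates are collected. The size depends entirely on assumed values: from almost nothing (5.3% against a nominal 5%) to 26% in the most unfavourable setting tabulated in step 2. Those rates are for the F test with one linear covariate. Kruskal-Wallis was not calculated separately, but it has no covariates either.

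A reader might infer three stronger things:

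- **That the groups will be imbalanced, or that altitude results will be false.** The documents give no imbalance and no correlation.
- **That the documents declare a non-randomised design.** They are silent, and the inference comes from the exposure.
- **That the repeated-measures ANOVA is distorted throughout.** A covariate that shifts all times equally leaves group-by-time at 5%. Only a covariate acting on the change over time affects that term, whereas the group main effect is exposed in both cases.

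**What to change.** Amend the SAP as follows.

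- **Non-repeated continuous outcomes** (such as time to T6, Bromage times, block durations): prespecify ANCOVA with altitude group, age, height and BMI, on the log scale if skewed and positive. Add ASA or say why it is left out. Report adjusted group differences with 95% confidence intervals as the main result and the currently planned tests as supportive.
- **Highest dermatome level and episode counts:** keep Kruskal-Wallis, labelled unadjusted.
- **Categorical outcomes:** keep chi-square, labelled unadjusted.
- **Repeated haemodynamic measurements:** name group-by-time as the tested term and report it also with covariate-by-time terms. Label any group-by-time result without those terms as unadjusted.
- **Conclusions:** word them as association. Only measured confounding is removed. If each altitude is a separate hospital, which the documents do not state, differences in site and staff would remain.

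The cost is SAP wording and some extra analysis in the SPSS package already named. No new data are needed and N stays at 93. Power is about 80% to 85% without systematic imbalance, about 77% to 84% under most of the imbalances modelled, and about 65% in the worst one. The SAP should state this possible loss.

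### The SAP gives the chi-square test no fallback for small expected counts, so with 31 women per group its p-values are unreliable for uncommon categorical outcomes

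*SAP*

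**What the plan says.** The closing paragraph of the SAP (the one that begins with the sample size) names a single method for categorical data: the chi-square test "will be used in the analysis of categorical variables". The threshold follows: "Statistical significance level will be accepted as p<0.05". No exact test, Monte Carlo option or minimum expected count is mentioned. In the same paragraph, continuous variables do have a fallback, the Kruskal-Wallis test, for when parametric assumptions fail.

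Several outcomes fall under the categorical rule. The protocol's data form has "Postdural puncture headache follow-up (YES/NO") at day 1 and day 7, and a four-grade nausea-vomiting scale. The Study design text adds that "the highest level of sensory block, and anesthetic complications will be recorded", and that by phone "the patients will be questioned by the researcher for postdural puncture headache". Neither document gives an expected rate for any of these.

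The group size is fixed by the ANOVA power calculation: the SAP's Summary Statements say that "sample sizes of 31, 31, and 31 are obtained from the 3 groups whose means are to be compared", and the closing paragraph repeats that the number "was calculated as 31 for each group, a total of 93".

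**The concern.** The chi-square p-value is a large-sample approximation, and a common working limit for it is an expected count of 5 per cell. Groups of 31 fall short of that for any outcome with an overall risk under about 16%. Breaking complications down by type, or nausea-vomiting by grade, makes the cells sparser still.

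At stake are the between-altitude comparisons of headache, complications and severe nausea. If the rule is followed as written, the reported p-value can be about half its exact value, and in one plausible table it lands on the wrong side of 0.05. If the analyst instead departs from the rule on seeing a sparse table, the test has been chosen after seeing the data.

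**Working it through.** **Inputs.** From the SAP: three groups, 31 per group, N = 93, alpha 0.05, SD of means 18.37, within-group SD 55.35, stated power 0.81163. From the protocol: headache is recorded yes/no. Assumed, because the documents give no figure: a common event risk of 2 to 5%.

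**The plan's own figure.** Effect size = 18.37/55.35 = 0.3319. Noncentrality = 93 × 0.3319² = 10.24. The noncentral F with 2 and 90 df gives power 0.8116, matching the stated 0.81163; 30 per group gives 0.797. So 31 per group is correct for the ANOVA and is the group size to use here.

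**When are expected counts below 5?** With t events in total, each group's expected count is t/3. This reaches 5 only at t = 15, and 15/93 = 16.1%.

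**Chi-square against exact p, all events in one group.** The Pearson statistic has 2 df, so p = exp(−X²/2). The exact p for t/0/0 is 3·C(31,t)/C(93,t), because here only the three arrangements of that split are as improbable as the one observed.

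- 3/0/0: expected events 1, non-events 30. X² = (4+1+1)/1 + (4+1+1)/30 = 6 + 0.2 = 6.2, p = exp(−3.1) = 0.045. Exact p = 3 × 4,495/129,766 = 0.104.
- 4/0/0: X² = 8 + 0.36 = 8.36, p = 0.015. Exact p = 94,395/2,919,735 = 0.032.
- 5/0/0: X² = 10 + 0.57 = 10.57, p = 0.005. Exact p = 509,733/51,971,283 = 0.010.

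For 3/0/0 the Fisher-Freeman-Halton test and the exact test ordered by the Pearson statistic agree, so that result does not depend on which exact test is used.

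**How often does the verdict change?** Enumerating every split of one to nine events over 31/31/31, chi-square and Fisher-Freeman-Halton disagree at 0.05 only for 3/0/0. For example, 5/1/0 gives 0.024 against 0.044 and 6/1/1 gives 0.033 against 0.046, with the same verdict both times.

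**How likely is that table with no altitude effect?** The total is exactly three with probability 16.8%, 22.6% and 16.0% at risks of 2%, 3% and 5%. Multiplying by 0.104, the chance that all three fall in one group, gives about 1.8%, 2.3% and 1.7% of trials.

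**Overall size of the chi-square test** (three equal binomial risks, all totals):

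| Common risk | Size |
|---|---|
| 0.5% | 0.001 |
| 2% | 0.021 |
| 3% | 0.032 |
| 5% | 0.036 |
| 8% | 0.037 |
| 10% | 0.041 |
| 20% | 0.050 |

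**The case against.** The strongest reply is that the planned test does little harm in practice. Its size, averaged over event totals, is at or below about 5% at every risk checked, and one table among totals of one to nine changes verdict. The sample size rests on a continuous outcome, no hypothesis is attached to headache or complications, and rarity is an assumption. The usual replacement is also far from free: Fisher-Freeman-Halton has an unconditional size of only 0.3%, 0.8% and 1.9% at risks of 2%, 3% and 5%. At larger totals the disagreement can also run the other way: 5/5/0 gives chi-square 0.061 and Fisher-Freeman-Halton 0.043.

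All of that stands, and it rules out two stronger readings. A reader might infer that the chi-square rule inflates the false-positive rate. It does not: the 10.4% rejection rate applies only given exactly three events, and given four, five or seven events it is 3.2%, 1.0% and 1.5%. A reader might also infer that any handful of cases at one altitude would be falsely called significant. The 4/0/0 and 5/0/0 splits are significant under the exact test too.

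The reply does not remove the defect. The reported p-value is still wrong in sparse tables, and the SAP gives the analyst no rule for them, although it gives one for non-normal continuous data.

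**Conclusion.** The concern holds as an omission with a limited effect. Under the SAP as written, any categorical outcome affecting fewer than 15 of the 93 women is tested with an approximation outside its usual range. The clearest consequence is 3/0/0, reported as p=0.045 when the exact value is 0.104. With no altitude effect, that table would arise in roughly 2% of trials for each outcome with a true risk of 2 to 5%. For 4/0/0 and 5/0/0 the p-value is about half the exact one, but the conclusion is unchanged.

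The 16% threshold and the p-values follow from the documents' group sizes alone. That the trial will meet such tables rests on the assumed risks, which the documents neither support nor contradict. The sample size is unaffected. The change should be made because it is cheap and settles the test before the data are seen; the trial's main comparisons do not depend on it.

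**What to change.** Add one sentence to the SAP: if any expected count in a table is below 5, the Fisher-Freeman-Halton exact test (Fisher's exact test for two groups) replaces the chi-square test, including for pairwise comparisons. Monte Carlo sampling may be used only to compute that same test. A single test should be named because exact tests that order the tables differently can disagree at larger event totals.

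The cost is one sentence, with no change to sample size or data collection. If the exact-test option is not licensed in the planned SPSS version, free software can run it. The statistical price is real conservatism when events are very few: with three events in total the exact test cannot reach p<0.05, however they are split. Counts and percentages by group should therefore be reported alongside the p-value.

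How the day 1 and day 7 headache answers are combined for each woman is a separate gap in definition, which this sentence does not settle.

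### The repeated-measures ANOVA for MAP, HR and SpO2, read naturally, drops a patient from every time point if one of eight readings is missing; a mixed model in the same software would not

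*SAP*

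**What the plan says.** **Schedule.** The protocol's Study design section records MAP, HR and SpO2 at baseline and "at the 3rd, 5th, 10th, 15th, 30th, 45th and 60th minutes after the procedure". That makes eight readings per variable.

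**Form.** The data form puts all eight in one grid headed "INTRAOPERATIVE" follow-up. Its postoperative part covers block end times, nausea and vomiting, and headache, with no separate field for vital signs.

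**Timing of surgery.** "surgery will be started by recording the time to reach T6 dermatome", so time in theatre after the spinal includes the wait for the block as well as the operation. Operation time is recorded, but no expected length is given. A recovery-room stage precedes the ward.

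**Analysis.** The SAP's closing paragraph assigns one-way ANOVA or Kruskal-Wallis to continuous variables. A separate sentence then says that ANOVA "will be used for repeated measurements at different times between groups". The only software statement is that the SPSS "22.0 program will be used in the analysis of the data obtained in the study". No SPSS procedure, missing-reading rule or dropout allowance is given.

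**Sample size.** The SAP describes 31 per group, 93 in total, as "The minimum number of patients required to complete our study with 95% confidence level" and 80% power.

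**The concern.** One-way ANOVA already has its own sentence, so the separate sentence on repeated measurements most naturally means a group-by-time repeated-measures ANOVA. In SPSS the standard route is GLM Repeated Measures. It takes one row per patient with a column for each time, and it deletes the whole row if any column is empty.

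A patient lacking only the 60-minute value would therefore lose seven recorded readings of that variable, and one lacking both the 45- and 60-minute values would lose six. The discarded values include baseline and the first minutes after the spinal. Haemodynamic change is in the study title, so precision on these variables matters. If missingness were also related to group and outcome, the patients left in the analysis would no longer represent their groups.

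**Working it through.** **1. The plan's own figure.** Inputs from the SAP's Numeric Results: k = 3, n = 31 per group, Sm = 18.37, S = 55.35, alpha = 0.05.

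- Effect size f = 18.37 / 55.35 = 0.3319.
- Noncentrality = N × f² = 93 × 0.3319² ≈ 10.24, with 2 and 90 degrees of freedom.
- Noncentral F power = 0.8116, against 0.81163 stated, so the figure reproduces. With 30 per group it is 0.797, so 31 is the smallest size reaching 80% for that test.

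This is a one-way test on a variable the SAP does not name. Power for a repeated-measures test also depends on the correlation among readings, which is not given. The figure therefore cannot be carried over to MAP, HR or SpO2.

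**2. Patients lost to scattered misses.** The per-reading miss rate p is an assumption; the eight readings come from the protocol.

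- If misses are independent, the share of patients with at least one missing reading is 1 − (1 − p)⁸.
- p = 2%: 1 − 0.98⁸ = 0.149, or 0.149 × 93 ≈ 14 patients.
- p = 5%: 1 − 0.95⁸ = 0.337, or 0.337 × 93 ≈ 31 patients.
- At the other extreme, if all misses fall in patients who miss all eight, only 2% or 5% of patients go. The ranges are thus 2% to 15% and 5% to 34%.

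**3. Recorded data discarded under independent misses.** Each variable has 93 × 8 = 744 scheduled readings.

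- p = 2%: 0.149 × 744 ≈ 111 readings leave the analysis. About 0.02 × 744 ≈ 15 were truly missing, so about 96 recorded values are thrown away.
- p = 5%: 0.337 × 744 ≈ 250 leave. About 37 were truly missing, so about 213 recorded values are thrown away.

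**4. When deletion biases the group comparison.** Suppose, purely for illustration, that readings stop at theatre exit. Exit time is normal with SD 12 minutes and mean 55 minutes in the first group, MAP in SD units has correlation ρ with exit time, and only patients still present at 60 minutes are kept. The retained mean shifts by ρ × φ(z) / (1 − Φ(z)), with z = (60 − mean) / 12. A simulation under these assumptions gave:

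- ρ = 0: no shift in any group, whether or not exit times differ. Only precision is lost.
- ρ = 0.3, same exit times in all groups: about 34% kept, and every group shifts by about 0.32 SD. The contrast is unchanged.
- ρ = 0.3, mean exit times 6 minutes apart (55, 61, 67): about 34%, 53% and 72% kept, with shifts of 0.33, 0.23 and 0.14 SD. A false difference of 0.326 − 0.142 ≈ 0.18 SD appears between the outer groups.

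Bias needs both conditions: exit time related to the outcome, and exit time different between groups. The documents establish neither.

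**The case against.** The strongest objection is that nothing shows late readings will be missing. The protocol schedules the 60-minute reading without exception and describes a recovery room where it could be taken. The form's grid is defined by minutes after the spinal, so its last columns can be filled anywhere. Its heading is not literal either, since the same grid holds the baseline. This stands. A reader might infer that patients with short operations are dropped and that the loss follows surgery time. The documents do not support that: they give no operation length, do not say that readings stop at theatre exit, and start surgery only once the block reaches T6, so onset time would count as well.

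Second, the SAP does not name the SPSS procedure. ANOVA at each time point, or the MIXED procedure, would not remove whole patients. This is true, but neither is the natural reading of the sentence, and the text leaves it open.

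Third, a reader might put reduced group sizes into the SAP's power calculation and report, for example, a fall from 81% to 50% at 16 per group. The arithmetic is right (0.499), but the table names no variable and describes a one-way test. If the sized outcome is a single block time, its power is untouched by a missing 60-minute pressure. Likewise, the phrase about completing the study may mean carrying it out rather than counting completers, so it is weak evidence on slack.

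Fourth, episodes of hypotension treated with ephedrine are counted separately, and listwise deletion does not affect that count. This is correct, but it does not replace the comparison of MAP, HR and SpO2 over time.

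**Conclusion.** The point holds as a weakness in the analysis method and its specification. On its natural reading, the plan discards every reading of a variable from any patient with one gap in eight, and no rule for missing readings offsets this. At assumed independent miss rates of 2% and 5% per reading, about 15% and 34% of patients would go, and fewer if misses cluster. None of this requires anyone to leave theatre early.

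Two stronger conclusions are not supported. Loss driven by early theatre exit is conditional on readings stopping there. Even then, between-group bias arises only if time to T6 plus operation time relates to the outcome and differs by altitude group; otherwise the cost is precision. No figure can be given for the power lost on these outcomes.

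The change should be made because it is cheap and recovers data already collected. Confidence is medium, since the SPSS procedure is inferred and the missing-reading rate is unknown.

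**What to change.** - **SAP.** Replace the repeated-measures sentence with a linear mixed model (SPSS MIXED) for each of MAP, HR and SpO2. Include group, time and group-by-time, prespecify the covariance structure, and state that all available readings are used.
- **SAP.** Add that missing readings will be reported by group and time point, so that any pattern is visible.
- **Form.** Change the heading of the vital-signs grid so that the 45- and 60-minute values are clearly entered whether the patient is in theatre or recovery.

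The cost is a couple of sentences and one form heading, with no change of software. The downside is that a covariance structure must be chosen in advance. The form change may prevent much of any late loss, but it does not deal with scattered misses, so the model change is still worth making. The mixed model also relies on the gaps being explained by the data observed, which is another reason to report them.
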